5.6.3.2 Urinalysis

Urinalysis is assessed, using dipsticks, at the same visits as biochemistry and hematology.

Urinalysis results will be listed only.

5.6.3.3 Pregnancy Test and Urine THC Screen

Serum pregnancy test results and urine THC screen results will be summarized by treatment arm and visit.

5.6.4 Vital Signs, Other Physical Findings and Other Safety Data

5.6.4.1 Vital Signs

At Visit 1, 3 and B3, systolic and diastolic blood pressure are collected in the sitting, supine and standing positions. At all other visits, systolic and diastolic blood pressure are collected in the sitting position only.

Summaries will be presented by treatment arm for each vital sign parameter at each visit. Change from baseline to each post-baseline visit will also be presented.

Body mass index will be calculated, for each visit in which height and weight are recorded, as:

$$\text{Weight (kg)} \div \text{height (m)}^2$$

A separate table will be produced, by treatment arm and visit, presenting the incidence of patients with vital signs indicative of a medical condition at Visit 1 and indicative of an adverse event after Visit 1.

Based on the criteria presented in Section 8, clinically significant changes from baseline in vital signs measurements and other defined flagged values will be identified at each visit. The number of patients with a clinically significant change from baseline will be summarized by parameter, visit and treatment arm. The number of patients with at least one post-baseline flagged vital sign parameter value will be summarized by parameter, flagged criteria and treatment arm for the blinded phase and repeated for the OLE phase.

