3. INVESTIGATIONAL PLAN

3.1 Trial Design

This multicenter trial consists of a randomized, placebo-controlled, double-blind phase followed by an open-label extension (OLE) phase.

Blinded Phase:

The blinded phase of the trial is a randomized, double-blind, parallel-group, 16-week comparison of two doses of GWP42003-P vs. placebo. Patients will complete a 1-week screening period and a 4-week baseline period before they are randomized to receive either 25 mg/kg/day GWP42003-P, 50 mg/kg/day GWP42003 P or placebo. Randomization will be stratified by age according to the following ranges: 1–6, 7–11, 12–17 years and 18–65 years. Patients will begin a 4-week dose escalation period, titrating up to their assigned dose, before continuing on a stable dose of blinded Investigational Medicinal Product (IMP) for 12 weeks.

Dose escalation for each patient is subject to the investigator's assessment of safety and tolerability. If a dose becomes poorly tolerated, the investigator may consider temporarily or permanently reducing the dose for the remainder of the trial.

Following completion of the blinded phase, patients will be invited to continue to receive GWP42003-P in an OLE.

Those patients opting not to enter the OLE will complete a 10-day taper period (down-titrating 10% per day for 10 days).

Open-label Extension Transition:

In order to maintain consistent exposure to IMP and maintain the integrity of the blind, patients will enter a 2-week blinded transition to the OLE. OLE IMP will be titrated up to 25 mg/kg/day whilst blinded IMP is simultaneously tapered down to zero. All patients will complete the transition and enter the OLE taking 25 mg/kg/day GWP42003-P:

- Patients from the placebo arm will titrate up to 25 mg/kg/day GWP42003-P.
- Patients from the 25 mg/kg/day GWP42003-P arm will continue to take 25 mg/kg/day GWP42003-P.
- Patients from the 50 mg/kg/day GWP42003-P arm will taper down (10% per day) to 25 mg/kg/day GWP42003-P.

Open-label Extension:

The OLE consists of a 3-week titration period followed by a maintenance period and a 10-day taper period. The initial OLE period will last for a maximum of 1 year.

Following titration according to the titration schedule, patients will continue with their optimal GWP42003-P dose. However, investigators may decrease the dose if a patient experiences intolerance, or increase the dose to a maximum of 50 mg/kg/day if required for better seizure control, until the optimal dose is found.

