3.2 Definition of Sample Size

Blinded Phase:

A total of 210 patients will be enrolled. The 210 patients will be randomly allocated to 1 of 4 treatment arms (GWP42003-P 25 mg/kg/day, GWP42003 P 50 mg/kg/day, placebo 25 mg/kg/day dose volume equivalent, or placebo 50 mg/kg/day dose volume equivalent) at a 2:2:1:1 ratio. The placebo arms will be pooled for the analyses of efficacy.

If it is assumed that patients in the placebo arm will experience a mean reduction in seizure frequency of 15% (from baseline), patients receiving GWP42003-P will experience at least a 50% reduction in seizures and a common standard deviation of 60%, then this sample size of 70 patients per arm will be sufficient to detect a difference in response distributions with 90% power. This test is based on a two-sided non-parametric Mann-Whitney-Wilcoxon test for continuous response data with a 5% significance level.

Open-label Extension:

All patients who wish to continue on IMP following the blinded phase.

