For eGFR, results will be assigned to the following grades:

- Normal: $>60 \text{ ml/min/1.73 m}^2$
- Grade 1: $60 \text{ ml/min/1.73 m}^2$
- Grade 2: ≥ 30 and $<60 \text{ ml/min/1.73 m}^2$
- Grade 3: ≥ 15 and $<30 \text{ ml/min/1.73 m}^2$
- Grade 4: $<15 \text{ ml/min/1.73 m}^2$

A separate shift table will be produced for eGFR based upon the above grades to determine the categorical shifts from baseline to each post-baseline visit.

For the blinded phase, scatter plots will be produced for each laboratory parameter presenting the maximum post baseline result divided by the upper limit of normal (ULN) on the Y-axis, and the baseline result divided by the ULN on the X-axis. However, for prothrombin international normalized ratio (INR), both axes will present the raw results rather than dividing by ULN.

An additional table will be produced for the blinded phase only, summarizing the number of patients meeting the following criteria:

- Alanine aminotransferase (ALT) $> 1 \times \text{ULN}$ at baseline
- Aspartate aminotransferase (AST) $> 1 \times \text{ULN}$ at baseline
- AT $> 1 \times \text{ULN}$ at baseline
- Treatment emergent ALT $> 3 \times \text{ULN}$, $> 5 \times \text{ULN}$ and $> 8 \times \text{ULN}$
- Treatment emergent AST $> 3 \times \text{ULN}$, $> 5 \times \text{ULN}$ and $> 8 \times \text{ULN}$
- Treatment emergent AT $> 3 \times \text{ULN}$, $> 5 \times \text{ULN}$ and $> 8 \times \text{ULN}$
- Treatment emergent AT $> 3 \times \text{ULN}$ and either bilirubin $> 2 \times \text{ULN}$ or INR > 1.5

where AT is AST or ALT, and treatment emergent is defined as criteria not met at baseline but met at any time post-baseline. The above will be summarized overall and for the following subgroups:

- Sex (Male, Female).

- Valproic acid use (Yes, No).
- Clobazam use (Yes, No).
- Valproic acid use and Clobazam use (Yes/Yes, Yes/No, No/Yes, No/No).
- Patients taking 3 or more current AEDs.
- Patients taking 4 or more current AEDs.

A separate table will be produced, by treatment arm and visit, presenting the incidence of patients with urinalysis or blood results indicative of a medical condition at Visit 1 and indicative of an adverse event after Visit 1.

All laboratory data will be listed; listings will include limited demographic information about the patient (age, sex, race and weight at baseline). Abnormal laboratory values will be listed separately.

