8. ATTACHMENTS AND APPENDICES

Appendix 1 Adverse Events of Special Interest – Abuse Liability

Withdrawal	Drug withdrawal convulsions
	Drug withdrawal headache
	Drug withdrawal maintenance therapy
	Drug withdrawal syndrome
	Drug withdrawal syndrome neonatal
	Drug rehabilitation
	Rebound effect
	Steroid withdrawal syndrome
	Withdrawal arrhythmia
	Withdrawal syndrome

Drug abuse and dependence	Dopamine dysregulation syndrome
	Drug abuse
	Drug abuser
	Drug dependence
	Drug dependence, antepartum
	Drug dependence, postpartum
	Intentional drug misuse
	Intentional overdose
	Maternal use of illicit drugs
	Neonatal complications of substance abuse
	Polysubstance dependence
	Substance abuse
	Substance abuser
	Accidental overdose
	Dependence
	Disturbance in social behaviour
	Drug administered at inappropriate site
	Drug detoxification
	Drug diversion
	Drug level above therapeutic
	Drug level increased
	Drug screen
	Drug screen positive
	Drug tolerance
	Drug tolerance decreased
	Drug tolerance increased
	Medication overuse headache
	Narcotic bowel syndrome
	Needle track marks
	Overdose
	Prescribed overdose
	Prescription form tampering
	Substance use
Substance-induced mood disorder	
Substance-induced psychotic disorder	
Toxicity to various agents	

Appendix 2 Ranges for Clinically Significant Changes and Other Defined Flagged Values in Vital Signs

The range of values that will be used to identify clinically significant changes in vital signs parameters (See Section 5.6.4.1) are presented in Table 9.

Table 9 Ranges for Clinically Significant Changes in Vital Signs

Vital Sign	Range
Sitting Systolic BP	Change: < -20, > 20
Sitting Diastolic BP	Change: < -10, > 10
Pulse Rate	Change: < -10, > 10
Weight	Percent Change: $\leq -7, \geq 7$

Defined flagged values that will be used to identify low or high vital signs parameters (See Section 5.6.4.1) are presented in Table 10.

Table 10 Other Defined Flagged Values for Vital Signs

Vital Sign	Flag
Sitting Systolic BP	< 90, > 140, > 160
Sitting Diastolic BP	< 50, > 90, > 100
Pulse Rate	< 60, > 100
Temperature	> 38.0, < 36.0
Respiratory Rate	< 12, > 20

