Appendix 4 Toxicity Criteria for Laboratory Parameters

The toxicity criteria that will be used to identify abnormal laboratory parameters are presented in Table 12 and

Table 13.

Table 12 Toxicity Criteria for Biochemistry Parameters

Parameter	Toxicity Decrease	Toxicity Increase
Chloride	≤0.96xLL	≥1.04xUL
Calcium	≤0.89xLL	≥1.16xUL
Sodium	≤0.96xLL	≥1.04xUL
Potassium	≤0.90xLL	≥1.10xUL
Glucose (mmol/L)	≤3.2	≥16
Phosphate	≤0.79xLL	
Cholesterol	≤0.85xLL	≥1.6xUL
AST		≥3xUL
ALT		≥3xUL
Lactate Dehydrogenase		≥2.6xUL
Alkaline phosphatase		≥2xUL
Gamma GT		≥2.6xUL
Bilirubin		>2xUL
Albumin	≤0.84xLL	
Total protein	≤0.84xLL	≥1.16xUL
Urea		≥2.6xUL
Blood urea nitrogen		≥2.6xUL
Creatinine		≥2.6xUL
Uric acid		≥1.16xUL

UL = upper limit of reference range

LL = lower limit of reference range

Table 13 Toxicity Criteria for Hematology Parameters

Parameter	Toxicity Decrease	Toxicity Increase
Hemoglobin (g/dL)	≤9.4	
Hematocrit (%)	≤28	
Red cell count	≤0.84xLL	
Mean corpuscular volume	≤0.84xLL	≥1.11xUL
Mean corpuscular hemoglobin	≤0.84xLL	
Mean corpuscular hemoglobin concentration	≤0.84xLL	
Platelets (x10 ⁹ /L)	≤74	
Prothrombin time		>1.5xUL
Prothrombin international normalized ratio		>1.5
Total white blood cell count (x10 ⁹ /L)	≤2.9	≥21
Total neutrophil count (x10 ⁹ /L)	≤1.36	≥14.7
Segmented neutrophil count (x10 ⁹ /L)	≤0.75	≥12.3
Eosinophils (x10 ⁹ /L)		≥1.5
Basophils (x10 ⁹ /L)		≥0.31
Monocytes (x10 ⁹ /L)		≥2.1
Lymphocytes (x10 ⁹ /L) for patients <18 years (auto hematology)	≤1.0	
Lymphocytes (x10 ⁹ /L) for patients <18 years (manual hematology)	≤0.2	
Lymphocytes (x10 ⁹ /L) for patients ≥18 years	≤0.2	

UL = upper limit of reference range

LL = lower limit of reference range

Appendix 5 Derivation Instructions for Achenbach Child Behavior Checklists and Adult Behavior Checklist

CBCL/1½–5

The syndrome scale and problem scale grouping of items is shown in Table 14. If data are missing for more than 8 items (not counting item 100) then the syndrome and problem scales will not be calculated.

Each of the items is scored 0, 1 or 2 as indicated on the questionnaire. The individual items associated with each syndrome scale are presented in Table 14.

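### The vital-sign flag table uses one set of limits for ages 1 to 65 and counts flags already present at baseline, which dilutes arm differences in several rows (minor)

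*SAP*

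**What the plan says.** The population is wide. Section 3.1 states: "Randomization will be stratified by age according to the following ranges: 1–6, 7–11, 12–17 years and 18–65 years". Three of the four strata are under 18.

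Appendix 2 introduces the limits thus: "Defined flagged values that will be used to identify low or high vital signs parameters (See Section 5.6.4.1) are presented in Table 10". Table 10 gives one set for everyone:

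- sitting systolic below 90, above 140, above 160
- sitting diastolic below 50, above 90, above 100
- pulse below 60, above 100
- temperature below 36.0, above 38.0
- respiratory rate below 12, above 20

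Section 5.6.4.1 fixes the count: "The number of patients with at least one post-baseline flagged vital sign parameter value will be summarized by parameter, flagged criteria and treatment arm". It is produced for the blinded phase and repeated for the OLE. No condition on the baseline value is given. The output list in Appendix 6 (Table 14.1.3 and OLE Table 14.1.3) shows no split by age.

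The same section plans other vital-sign outputs. Beside the by-visit summaries, "Change from baseline to each post-baseline visit will also be presented", and "The number of patients with a clinically significant change from baseline will be summarized by parameter, visit and treatment arm". Table 9 defines that last count for systolic and diastolic pressure, pulse and weight. Respiratory rate and temperature are not in it.

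Elsewhere the SAP conditions on baseline. For the liver criteria in Section 5.6.3.1, "treatment emergent is defined as criteria not met at baseline but met at any time post-baseline". It also uses age elsewhere: Appendix 4 gives separate lymphocyte limits below and from 18 years, and Section 5.7.2 repeats AUC summaries by stratified age group.

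**The concern.** A safety flag table is read across arms for an excess on active treatment. A patient who met the flag before the first dose, and still meets it later, is counted in every arm regardless of treatment. A small child whose ordinary resting pulse is above 100 is counted in the same way. Both add a background that carries no information about the drug.

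The rule of at least one value adds to this, because the chance of a flag grows with the number of readings. A real effect on pulse, respiration or blood pressure would then look smaller than it is. In the OLE all patients take active drug, so no concurrent placebo group shows how much of the count is background.

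**Working it through.** The SAP states no rate or power for this table, and no test is planned on it, so there is no figure to reproduce. The checks below are illustrations.

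**1. Dilution by flags present at baseline.** Let c be the share of each arm already flagged at baseline and still flagged afterwards, and r the rate of new flags among the rest. The planned count is p = c + (1 − c)r, so the arm difference is (1 − c)(r₁ − r₀).

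Inputs:
- 70 patients per arm (Section 3.2; pooled placebo).
- r₀ = 10% and r₁ = 30%: assumed.
- Share aged 1–6: 20% to 40%, assumed.
- Share of these already flagged: 50% to 90%, assumed.
- Share of older patients already flagged: 5%, assumed.

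Trial-wide, c runs from 0.2 × 0.5 + 0.8 × 0.05 = 0.14 to 0.4 × 0.9 + 0.6 × 0.05 = 0.39. Power of a two-sided 5% comparison of proportions serves here only as a yardstick.

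| c | planned count, placebo vs active | difference | power, any flag | power, unflagged at baseline only |
|---|---|---|---|---|
| 0 | 10% vs 30% | 20 points | 0.85 | 0.85 |
| 0.14 | 22.6% vs 39.8% | 17.2 | 0.60 | 0.79 |
| 0.39 | 45.1% vs 57.3% | 12.2 | 0.30 | 0.64 |
| 0.90 | 91% vs 93% | 2 | 0.06 | 0.15 |

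The last row could describe some rows of the youngest stratum. It does not describe a whole arm under these assumptions.

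**2. Accumulation over visits.** Table 2 has six post-baseline clinic visits from Day 15 to Day 113 (Day 71 is by telephone). If visits were independent, a per-visit chance q gives 1 − (1 − q)⁶: 47% for q = 10%, 74% for 20%, 88% for 30%.

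**3. Pulse above 100 in a young child, no drug effect.** Assumed: group mean 95 to 110, between- and within-patient SD 8 each, one baseline and six later readings (simulation).

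| assumed mean | any later flag, all patients | newly flagged, of all patients | newly flagged, of those unflagged at baseline |
|---|---|---|---|
| 95 | 70% | 40% | 60% |
| 100 | 86% | 37% | 75% |
| 105 | 95% | 28% | 86% |
| 110 | 98% | about 18% | 93% |

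The denominator matters. At mean 110 only about 19% of patients are unflagged at baseline. The small figure in the third column arises because few remain at risk, not because the background has gone. Conditioning on baseline therefore does not by itself clear the age effect in young children.

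**The case against.** The strongest reply is that the comparison is still fair. Randomization is stratified by age, so background flags should be similar in each arm and the table is diluted rather than distorted. That largely stands. One qualification is that SAP addendum Section 2.3.3 reports more withdrawals in the active arms than on placebo. Fewer visits lower a count of at least one value: at assumed mean 95, three readings give 57% and six give 70%. The SAP gives no visit counts, so the size of this is unknown.

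Rows are also separate by criterion. Young age need not load pulse below 60, respiratory rate below 12 or the high blood pressure rows. Change from baseline, the Table 9 counts, a table of vital signs indicative of an adverse event (Table 14.1.4) and listings are planned too. That stands, except that Table 9 leaves out respiratory rate and temperature, so Table 10 is their only threshold count.

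The argument from inconsistency is moderate. The ECG flags in Section 5.6.4.2 follow the same rule, and the haemoglobin, platelet and white-cell limits in Appendix 4 are also fixed for all ages.

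A reader might infer that the table cannot show any treatment effect, or that it will sit near 100% in every arm. The documents do not support either. Arm totals pool all ages, and under the assumed age mix most of the difference survives. That most young children would be flagged is likewise an assumption, since the SAP gives no paediatric ranges and no age mix.

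**Conclusion.** The point holds as a minor weakness of a descriptive safety table. The text is clear: one set of limits for ages 1 to 65, and no baseline condition, whereas the SAP applies that condition to its liver criteria. The consequence is dilution in the rows for pulse above 100, respiratory rate above 20, systolic below 90 and diastolic below 50. Under the assumed 14% to 39% already flagged, 20 points shrink to about 17 to 12. Near-saturation is plausible only in some rows of the youngest stratum. It was checked for pulse alone, with assumed means and SDs. The OLE version is harder to read, because it has no comparator. Efficacy conclusions are not touched.

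**What to change.** In Section 5.6.4.1, for each criterion:

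1. Count a patient only if the flag was not met at baseline (Section 5.1.3.1) and was met afterwards, with patients unflagged at baseline as the denominator. State that denominator in the table.
2. Present Table 14.1.3 and OLE Table 14.1.3 by stratified age group as well as overall.

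The two belong together. Under the assumptions above, step 1 alone leaves 60% to 93% of eligible young children newly flagged for pulse without any drug effect. Age-specific reference limits are not needed for this point, and none are proposed here.

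No new data are required. The cost is one extra condition, an age split, longer tables and small cells: 70 patients over four strata average 17.5 per stratum and arm (70 ÷ 4), fewer once those flagged at baseline are removed. Using the pooled placebo column for the age split would limit this. No test is planned on the table, so the change adds no multiplicity.

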5.6.4.2 Electrocardiogram

Summaries will be presented by treatment arm for ventricular rate, PR interval, QRS duration, QT interval and QTcB, at each visit. Change from baseline to each post-baseline visit will also be presented.

A separate table will be produced, by treatment arm and visit, presenting the incidence of patients with an ECG indicative of a medical condition at Visit 1 and indicative of an adverse event after Visit 1.

Based on the criteria presented in Section 8, defined flagged values will be identified at each visit. The number of patients with at least one post-baseline flagged ECG parameter value will be summarized by parameter, flagged criteria and treatment arm for the blinded phase and repeated for the OLE phase.

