Appendix 3 Defined Flagged Values in ECG Parameters

Defined flagged values that will be used to identify low or high ECG parameters (See Section 5.6.4.2) are presented in Table 11.

Table 11 Defined Flagged Values for ECG Parameters

ECG Parameter	Flag
QTc	> 450, > 480, > 500

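### QTcB is the only corrected QT specified, and the QTc flags count any post-baseline exceedance regardless of baseline, which makes them hard to interpret, most of all in the open-label extension

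*SAP*

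**What the plan says.** SAP Section 5.6.4.2 sets the continuous ECG output: "Summaries will be presented by treatment arm for ventricular rate, PR interval, QRS duration, QT interval and QTcB, at each visit". It adds: "Change from baseline to each post-baseline visit will also be presented". QTcB is the only corrected QT named in the SAP or its addendum.

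For the categorical output the same section says: "The number of patients with at least one post-baseline flagged ECG parameter value will be summarized by parameter, flagged criteria and treatment arm". This is planned for the blinded phase and again for the open-label extension (OLE). Table 11 in Appendix 3 has a single row, labelled QTc with no correction named, and the limits "> 450, > 480, > 500" (no unit is given; milliseconds are taken here). The count is not conditioned on the baseline value, and no size of QTc increase is defined as a category.

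The SAP handles two other safety domains differently. For liver tests, Section 5.6.3.1 states that "treatment emergent is defined as criteria not met at baseline but met at any time post-baseline". For vital signs, Section 5.6.4.1 states: "The number of patients with a clinically significant change from baseline will be summarized by parameter, visit and treatment arm", with the limits in Table 9.

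On the population, Section 3.1 states: "Randomization will be stratified by age according to the following ranges: 1–6, 7–11, 12–17 years and 18–65 years".

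**The concern.** Because no other correction is defined, a programmer can apply the Table 11 limits only to QTcB. Bazett's formula divides QT by the square root of RR. If QT in fact follows RR more weakly than that, QTcB is too high at fast heart rates, and young children are the patients most likely to have them. A fixed limit of 450 ms then means different things at different heart rates.

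The counting rule adds to this. A patient already above a limit before dosing counts in the same way as one who crosses it on treatment. The flag table is therefore partly a description of the patients enrolled.

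In the blinded phase, the cost is a higher background against which a true excess has to be seen. In the OLE it is greater. There every patient takes active drug (Section 3.1), there is no concurrent control, and long-term safety is the primary objective (Section 2.1). That table alone cannot separate old or rate-driven exceedances from new ones.

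**Working it through.** The SAP states no figure that can be reproduced here. The check is algebra plus stated assumptions.

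**Inputs.** The flag limits are from Table 11. The age range is from Section 3.1. Heart rates, the QTcF distribution and the true QT-RR exponent are assumptions, because the SAP gives none. Appendix 2 does flag pulse rates above 100 and changes of more than 10, so rates and shifts of that size are within what the SAP provides for.

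**Formulas** (HR in bpm, RR = 60/HR)

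- QTcB = QT / (60/HR)^(1/2)
- QTcF = QT / (60/HR)^(1/3)
- Hence QTcB = QTcF × (HR/60)^(1/6)

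**Direct examples**

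- QT 320 ms at 120 bpm: QTcB = 320 × 2^(1/2) = 452.5 ms; QTcF = 320 × 2^(1/3) = 403.2 ms. The first is flagged and the second is not.
- QT 330 ms at 110 bpm: QTcB 446.8 ms, QTcF 403.9 ms. Neither is flagged.

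**QTcF at which QTcB reaches each limit** (limit divided by the factor)

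| HR | Factor (HR/60)^(1/6) | 450 | 480 | 500 |
|---|---|---|---|---|
| 60 | 1.0000 | 450 | 480 | 500 |
| 80 | 1.0491 | 429 | 458 | 477 |
| 100 | 1.0889 | 413 | 441 | 459 |
| 120 | 1.1225 | 401 | 428 | 445 |
| 140 | 1.1517 | 391 | 417 | 434 |

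**Share above 450 ms**, assuming QTcF is normal with mean 400–410 ms and SD 15–20 ms

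- By QTcF: about 0.04–2.3%
- By QTcB at 80 bpm: about 3–17%
- By QTcB at 100 bpm: about 19–44%
- By QTcB at 120 bpm: about 48–73%

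**Effect of a heart-rate change alone**, QTcF held at 400 ms

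- 70 to 80 bpm: QTcB 410.4 to 419.6, a rise of about 9 ms
- 80 to 90 bpm: +8.3 ms
- 110 to 120 bpm: +6.5 ms
- 80 to 100 bpm: +15.9 ms

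**Sensitivity to the true exponent b.** A true QTc of 400 ms reads as QTcB = 400 × (HR/60)^(0.5 − b). At 120 bpm:

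- b = 0.33: 450 ms
- b = 0.40: 429 ms
- b = 0.50: 400 ms, so no inflation

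**Treatment of baseline across domains.** Liver flags require that the criterion was not met at baseline. Vital signs have absolute flags (Table 10) and also change criteria (Table 9). QTc has absolute flags only.

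**The case against.** The strongest reply is that the plan already holds what a careful reader needs. Section 5.6.4.2 presents ventricular rate, uncorrected QT and QTcB side by side, by arm and visit, each with change from baseline, so a shift in QTcB driven by heart rate can be recognised in the same table. ECGs indicative of an adverse event are tabulated by arm and visit, and ECG data are listed by patient. This stands. It rules out a reading that someone might take from the flag table alone, namely that QTc is assessed only by criteria that ignore baseline. What is missing is a categorical change criterion and a baseline condition on the flags.

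Secondly, randomization is stratified by age and the blinded safety tables have placebo columns. False flags common to all arms are background and not bias. A distortion between arms would need a treatment effect on heart rate, and the SAP suggests none. This also stands for the blinded phase. It does not carry over to the OLE.

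Thirdly, the size rests on assumed heart rates and on taking the cube-root relation as closer to the truth. This stands, and the inflation vanishes at an exponent of 0.5. Nor is every fast-rate child falsely flagged: the 110 bpm example stays below 450 ms, and at 120 bpm the two higher limits need a QTcF of about 428 and 445 ms. The inflation falls mainly on the lowest tier.

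Finally, the absolute vital-sign flags in Table 10 use the same rule of any post-baseline value, so the ECG rule follows a pattern in the SAP. That is true, but vital signs also have Table 9, and QTc has no counterpart.

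**Conclusion.** The point holds as a weakness in descriptive safety reporting. The SAP specifies one QT correction, leaves the correction in Table 11 unnamed, and counts QTc flags without regard to baseline.

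Under a cube-root QT-RR relation, the lowest flag is reached at a QTcF of about 429 ms at 80 bpm, 413 at 100 bpm and 401 at 120 bpm. At fast rates it therefore mainly reflects heart rate and age. With an exponent of 0.40 the inflation at 120 bpm is 29 ms on a QTc of 400 ms, compared with 50 ms at 0.33 and none at 0.50. The practical result is a raised background in all blinded arms and, in the OLE, a table that mixes pre-existing or rate-driven exceedances with new ones.

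A reader might infer that the flag table would be filled by young children, or that the cardiac-safety conclusion is unreliable. The SAP gives no heart rates, QT values or age mix to support the first. The planned change-from-baseline summaries and placebo columns argue against the second. Efficacy inference is unaffected.

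**What to change.** In Section 5.6.4.2 and Appendix 3:

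1. Derive QTcF = QT / (60/ventricular rate)^(1/3) from the QT and ventricular rate already collected, and summarize it with change from baseline beside QTcB.
2. Name the correction or corrections in Table 11, and apply the flags to QTcF as well as QTcB.
3. Count a flag as treatment-emergent only if it was not met at baseline, using the rule in Section 5.6.3.1. For the OLE, use the pre-randomization baseline that Section 3.3.2 already sets for that phase.
4. Add a categorical summary of QTc increase from baseline, by arm. Increases above 30 and above 60 ms are offered as examples. The SAP contains no such limits, so the sponsor should confirm them.

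The cost is SAP wording, one derived variable and a few extra ECG tables in each phase, with two sets of QTc results to report. No further ECGs are needed.
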